### **6.2.1 Anticipated Adverse Events**

A variety of complications are expected to occur in subjects undergoing CPB and cardiothoracic surgery, regardless of whether or not DrugSorb™-ATR is used. These may include, but are not limited to:

Serious, but less common, risks:

- Bleeding during or after the surgery including bleeding in relation to anticoagulation
- Blood clots that can cause heart attack, stroke, or lung problems
- Heparin-induced thrombocytopenia
- Bypass induced thrombocytopenia
- Reduction in platelets
  - Infection, including pneumonia
- Organ injury including:
  - Respiratory damage causing breathing problems or failure to wean from the ventilator
  - Cardiac dysrhythmias/arrhythmias
  - Kidney injury or renal failure
  - Cognitive impairment
- Death

Less serious, but more common risks and adverse events:

- Low-blood pressure
- Nausea and/or vomiting
- Hypothermia and/or Chills
- Allergic response to device materials
- Reduction in platelet count
- Reduction in white blood cell count
- Reduction in proteins (albumin, total protein)
- Coagulation within device
- Heparin-induced thrombocytopenia

### **6.2.2 Device-Related Adverse Events**

Potential adverse device events directly related to DrugSorb™-ATR:

- Removal of drugs and hormones
- Allergic response to device materials
- Reduction in platelet count
- Reduction in white blood cell count
- Reduction in proteins (albumin, total protein) which may increase with CPB duration.
- Reductions in serum calcium (as a consequence of reductions in albumin)
- Coagulation within device
- Infection
- Blood loss

- Hemolysis
- Device leakage
- Circuit leakage
- Death

### 6.2.3 Adverse Device Effect

An adverse device effect (ADE) is an AE related to the use of an investigational medical device. This definition includes AEs resulting from insufficient or inadequate instructions for use, deployment, installation, or operation, or any malfunction of the investigational medical device. The definition also includes any event resulting from use error or from intentional misuse of the investigational medical device. ADEs will be reported by the site and summarized by treatment group and overall.

### 6.2.4 Unanticipated Adverse Device Effect

An unanticipated adverse device effect (UADE) is any adverse device effect that by its nature, incidence, severity or outcome has not been identified in the current version of the risk analysis report. UADEs will be reported by the site and summarized by treatment group and overall.

## 6.3 Analyses of TEAEs

TEAEs will be summarized by the MedDRA® Preferred Term (PT) and by System Organ Class (SOC). Subjects reporting more than one AE within a SOC will be counted only once for that SOC. Subjects reporting the same AE more than once will be counted only once for that PT.

The severity of TEAEs will be presented in the TEAEs by severity table. If a Subject has the same TEAE on multiple occasions, the highest severity will be recorded for the TEAE.

An overview table will be summarized by treatment group and overall, which will include the number of subjects with any TEAEs, serious adverse events (SAEs), procedure related TEAEs, study device related TEAEs, TEAEs by severity, UADEs, device-related SAEs/Serious adverse device effect (SADE), serious UADEs (USADEs), procedure-related SAEs, SAEs leading to device discontinuation, TEAE(s) leading to death.

In addition, TEAEs will be summarized by treatment for the following:

- TEAEs by System Organ Class (SOC) and Preferred Term (PT)
- TEAEs by PT (descending order of frequency)
- TEAEs with  $\geq 5\%$  Incidence Overall by SOC and PT
- TEAEs by SOC, PT, and severity
- Device Related TEAEs/ Adverse Device Effect (ADE) by SOC and PT
- Procedure Related TEAEs by SOC and PT
- UADEs by SOC and PT

- SAEs by SOC and PT
- Device Related SAEs / Serious Adverse Device Effect (SADE) by SOC and PT
- Serious UADEs by SOC and PT
- Procedure Related SAEs by SOC and PT
- SAEs Leading to Device Discontinuation by SOC and PT
- SAEs Leading to Death by SOC and PT

Listings will be provided for all AEs, SAEs, TEAEs leading to device discontinuation, TEAEs leading to death.

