9.2. Safety and Tolerability Assessments

9.2.1. Adverse Events

Throughout the study, the Investigator or designee will determine adverse event (AE) occurrences. AE definitions, assignment of severity/seriousness/causality, and procedures for reporting SAEs, SADEs, and UADEs are detailed in Appendix 1.

The condition of each subject will be monitored from the time of signing the informed consent form (ICF; assent or consent) to the postoperative day 30 assessment. Subjects will be observed for any signs or symptoms and if possible, asked about their condition by open questioning, such as "How have you been feeling since you were last asked?", at least once each day while in hospital and at each investigation visit. Subjects will also be encouraged to spontaneously report AEs occurring at any other time during the investigation.

If an AE occurs, appropriate diagnostic and therapeutic measures are to be taken and the investigation treatment may be discontinued if appropriate. Follow-up evaluations of the subject are to be performed until the subject recovers or until the clinical Investigator considers the situation to be no longer clinically significant.

Adverse events are monitored and registered on the AE form of the eCRF. In absence of a specific diagnosis, an individual AE form has to be filled in for each sign or symptom. Changes from baseline laboratory values which are abnormal values and that are classified as clinically significant by the investigator (e.g., requiring medical intervention) must be recorded as AEs.

Persistent AEs will be entered once in the eCRF until they are resolved or if a new event has to be documented due to deterioration. These AEs will be carefully monitored. If an AE is still not resolved at the end of the investigation, this will be documented as ongoing. For recurrent AEs (i.e., AEs of the same nature, but with a different date of onset), an individual AE form has to be completed for each of them.

Bleeding event AEs

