11.6. Safety Analysis

All the safety endpoints will be analyzed in the SA Population. Additional safety analyses will be conducted on the mITT and PP Population if they are different from the SA population.

The incidence of all AEs occurring after the start of the CPB procedure will be summarized by treatment group using frequency and percentage. AEs that occur following informed consent but prior to the start of CPB will not be included in this safety analysis but will be provided in a listing. Within the Safety Analysis, AEs will be summarized by severity and relationship to the study device as determined by the Investigator (or designee). Discontinuations due to AEs, and SAEs will be summarized. All AEs will be coded using the Medical Dictionary for Regulatory Activities (MedDRA®) according to system organ class and preferred term, prior to database lock.

Observed values for clinical laboratory test data and vital signs, along with change from baseline results, will be summarized by collection time point. A summary of clinically notable values will be provided.

All the safety data will be listed in the SA population. Further details regarding presentation and analysis of safety data will be detailed in the SAP.

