11.8. Disposition and Baseline Characteristics

Number and percentage of subjects discontinuing prematurely from the study will be provided by treatment group and by reason discontinued. All data for background and demographic variables will be summarized and listed by treatment group and subject. Relevant medical history, current medical conditions, and incidence of prior and concomitant medications will be summarized by treatment group as well as listed.

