## **4 SUBJECT INFORMATION**

### **4.1 Disposition Information**

The number of subjects in each study population will be summarized by treatment. The number of subjects who did not receive a study device or were discontinued from the study will be summarized by treatment and the primary reasons for discontinuation will be provided.

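### SAP 6.3 tabulates device discontinuation only for serious adverse events, so no summary table counts device stops due to non-serious ones

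*SAP*

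**What the plan says.** Protocol 11.6 (Safety Analysis) states: "Discontinuations due to AEs, and SAEs will be summarized". It does not say whether the discontinuation is of the device or of the study.

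SAP 6.3 (Analyses of TEAEs) mentions device discontinuation in three places:

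- The overview table ends with "SAEs leading to device discontinuation, TEAE(s) leading to death".
- The tables by system organ class (SOC) and preferred term (PT) include "SAEs Leading to Device Discontinuation by SOC and PT".
- On listings, it says "Listings will be provided for all AEs, SAEs, TEAEs leading to device discontinuation, TEAEs leading to death".

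The first two are summaries and cover serious events only. The third covers events of any seriousness, but it is a subject-level listing.

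**The concern.** The primary safety endpoint in both documents is the GCP-level assessment of AEs, not of SAEs alone. How often the device had to be stopped because of an adverse event is a basic tolerability count, and stopping early also cuts exposure to the treatment. As SAP 6.3 is written, a subject whose device is stopped for a non-serious event adds nothing to either discontinuation table. A reader of the summary tables could take the serious-only figure for the full count of AE-related device stops.

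**Working it through.** The documents give no figure to reproduce and no rate to calculate from. The check is a comparison of text.

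**1. Can a non-serious AE lead to a device stop?** Yes, under the protocol's own rules. Protocol 9.2.1 says that after an AE "the investigation treatment may be discontinued if appropriate", with no condition on seriousness. Protocol Table 2 provides for ending exposure on unexpected signs of an allergic reaction, again without that condition. Stopping the device is not among the SAE criteria in Protocol Appendix 1, so a stop does not by itself make an event serious.

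**2. Does any other SAP table count such stops?**

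- SAP 4.1: "The number of subjects who did not receive a study device or were discontinued from the study will be summarized by treatment". A subject whose device is stopped during bypass, but who received it and stays in follow-up, is in neither group.
- SAP 4.6 summarises device exposure in minutes by treatment and accounts for interruptions. It shows shortened exposure but does not attribute it to an AE.
- SAP 6.3 tabulates all TEAEs and all device-related TEAEs by SOC and PT, whatever their seriousness. These tables count the event but do not show that it led to a stop.

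None of the three gives the number of subjects whose device was stopped because of a non-serious AE.

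**3. Is the restriction deliberate?** The SAP gives no reason for it. In the SAP 6.3 list, each of these categories has an all-event table and a serious-event table: TEAEs overall, device-related events, procedure-related events and UADEs. Discontinuation and death have only the serious version. For death nothing is lost, because an event that led to death is serious by definition. For discontinuation the restriction can drop events. The listing also uses the wider category, so the SAP recognises it without summarising it. This looks like a drafting slip.

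**4. Are the data available?** Yes. Under Protocol Appendix 1, the action taken for an AE is recorded in the eCRF, and the options include interruption and withdrawal of treatment.

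**5. Direction and scale.** The serious-only count can never exceed the all-TEAE count, so the tables can only understate. If all 70 subjects planned per arm are treated, each omitted subject is 1/70 = 1.4 percentage points. That is a scale, not a forecast.

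**The case against.** The strongest objection concerns what the protocol promised. A reader might infer that the SAP plainly breaks a protocol commitment to tabulate device stops. Protocol 11.6 does not say that. Protocol 4.4.4 and 11.8 use discontinuation for leaving the study, and if 11.6 means the same, the summary of reasons in SAP 4.1 meets it at least in part. This stands as a limit on the point. Against it, Protocol 11.8 already promises the study-level summary separately ("Number and percentage of subjects discontinuing prematurely from the study will be provided by treatment group and by reason discontinued"), which makes a second study-level meaning in 11.6 less likely but does not rule it out. The gap inside SAP 6.3, between its tables and its own listing, does not depend on how this is settled.

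Other objections also hold in part:

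- **Little is hidden.** Every TEAE that led to a device stop is listed. With up to 140 subjects, the count can be made by hand.
- **Many stops may be serious anyway.** Protocol Table 2 pairs the stop for an allergic reaction with aggressive treatment, and many such events would plausibly meet the SAE definition. The documents do not show how common non-serious stops would be.
- **A comparison between arms means little.** The sham is sealed and carries no blood, so the count matters mainly in the active arm.
- **Device deficiencies are a separate matter.** Protocol 2.1 allows flow to be stopped for a device quality complaint, which need not involve an AE. Such a stop would not enter an AE table and is not part of this gap.
- **The mock tables are in a separate document** (SAP 8) and may already include the row. The SAP text as written does not.

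**Conclusion.** The point holds as a small, specific reporting gap. SAP 6.3 limits both tabulations of device discontinuation to SAEs, and no other SAP table counts device stops due to non-serious AEs, whichever meaning Protocol 11.6 intended. The consequence is a summary count that may be too low, mainly in the active arm.

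The size cannot be estimated from the documents. A reader might infer that the tables will show zero while several subjects had the device stopped, but nothing in the documents supports any particular number. Nor are these events lost from the report, since they are listed, counted among all TEAEs, and reflected in the exposure summary when they shorten exposure. No endpoint, test, analysis population or data collection is affected.

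The conclusion rests on the SAP text alone and assumes that the separate table shells do not already carry the wider row.

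**What to change.** In SAP 6.3, change both entries, the overview row and the SOC/PT table, to TEAEs leading to device discontinuation, and keep SAEs as a sub-row. This brings the tables into line with the SAP's own listing and satisfies the device reading of Protocol 11.6. A short clarification of whether 11.6 means device or study discontinuation would remove the ambiguity.

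Device deficiencies without an AE should stay out of this table. They belong in the malfunction and deficiency summary by arm promised in Protocol 11.7.

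The cost is two table titles and one filter on data already collected and already listed.

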#### 6.4 Additional Safety Endpoints

The descriptive statistics will be presented by treatment group and overall, for the following additional safety endpoints.

- 30-day cardiac mortality
- 30-day all-cause mortality
- CEC-adjudicated bleeding event up to 30-day follow-up ( $30 \pm 5$  days)
- CEC-adjudicated postoperative stroke up to 30-day follow-up
- CEC-adjudicated postoperative myocardial infarction up to 30-day follow-up
- CEC-adjudicated urgent postoperative coronary revascularization up to 30-day follow-up

Data listings will be provided for the subjects with the observed data on the additional safety endpoints.

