This study is a prospective, multi-center, double-blind, randomized pivotal trial to evaluate the safety and effectiveness of the DrugSorb™-ATR device to reduce postoperative bleeding as measured by a composite endpoint of: fatal perioperative bleeding (occurring within 48hrs of the index operation), moderate, severe, or massive bleeding (UDPB ≥ 2), and 24-hour chest tube drainage in patients undergoing cardiothoracic surgery requiring CPB within two days of ticagrelor discontinuation. Subjects will be randomized in a 1:1 ratio to either standard of care (SOC) alone (control arm) or standard of care plus intraoperative ticagrelor removal with DrugSorb™-ATR integration in the CPB circuit (investigational arm). In the control arm a sham device that is not actively connected to the CPB circuit will be placed in the identical location as the DrugSorb™-ATR device in the investigational arm, with the entire set-up covered by a drape to maintain the

blind. Subjects will be followed out to 30 days after the surgical procedure for assessments of adverse events (AE) and survival.

Prior to randomization, subjects will be stratified based on a) site, and b) type of planned cardiothoracic surgery [either CABG alone, or all other surgeries (including but not limited to combination cardiac procedures, and aortic interventions)]. Stratification is intended to control for confounding effects arising from differing institutional practices and from procedure-specific CPB duration (i.e., device exposure – treatment duration) and bleeding risk.

Number of subjects:

Up to 140 subjects will be randomized into the study (70 into each arm).

Number of sites:

Approximately 30 investigational sites in the US and Canada will participate in the study.

Subjects must meet all inclusion criteria to be eligible to participate in the study. Subjects meeting any of the exclusion criteria are not eligible to participate in the study.

Inclusion criteria:

1. Males and females aged ≥ 18
2. Written full informed consent
3. Cardiothoracic surgery requiring CPB within two days of ticagrelor discontinuation (**last day of completed ticagrelor treatment** = day 0):
 - CABG alone
 - Valve repair or replacement
 - Combination surgery (i.e., CABG + valve operation)
 - Aortic surgery

Exclusion criteria:

1. Cardiothoracic surgery occurring 3 days or greater following ticagrelor discontinuation
2. Heart-lung transplant procedures

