The Intent-to-Treat (ITT) Population will include all subjects who are randomized. The modified Intent-to-Treat (mITT) Population will include all randomized subjects who undergo the index surgical procedure **and** receive a study device (whether DrugSorb™-ATR or *sham*). The primary analyses of the trial will be performed on the mITT Population. Baseline demographic and clinical variables will be summarized for each of the treatment groups in the mITT population. So long as the ITT and mITT populations are not identical, the ITT patients who do not fall within the mITT population will be presented in a listing, including the reasons for why they did not receive a study device. The Per Protocol (PP) Population will include all mITT subjects who have no major protocol violations. Analysis of the primary efficacy endpoint will be performed in the PP population as a supplemental analysis.

The Safety Analysis (SA) Population will include all enrolled subjects who are treated with a study device.

Safety Analysis

All the safety endpoints will be analyzed in the SA population. Additional safety analyses will be conducted on the mITT and PP Population if they are different from the SA population.

All AEs occurring after the start of the CPB procedure will be listed and summarized using descriptive methodology. The incidence of AEs will be presented by severity and by relationship to the investigational device (DrugSorb™-ATR or *sham*) as determined by the Investigator (or designee). Each AE will be coded using the Medical Dictionary for Regulatory Activities®. Observed values for clinical laboratory test data and vital signs, along with change from baseline results, will be summarized by collection time point. A summary of clinically notable values will be provided.

Safety oversight committees:**DSMB:**

Three physicians with relevant clinical/medical and investigational expertise together with an independent statistician will form the Data Safety Monitoring Board (DSMB). The primary role of the DSMB is to oversee the safety of subjects enrolled in the study. All DSMB members will be independent from the investigative sites and the study sponsor. The schedule and process associated with DSMB activities will be outlined in the DSMB charter.

CEC:

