4. INVESTIGATIONAL PLAN

4.1. Study Objective(s)

Patients undergoing cardiothoracic surgery within two days of ticagrelor discontinuation are at increased risk of bleeding complications due to platelet dysfunction. The DrugSorb™-ATR hemoadsorption device removes circulating ticagrelor at rates much higher than normal washout, thus reducing platelet dysfunction, improving hemostasis, and reducing postoperative blood loss.

The objectives of this study are as follows:

- To demonstrate reductions in postoperative bleeding with the intraoperative use of DrugSorb™-ATR in patients undergoing cardiothoracic surgery with CPB within two days of ticagrelor discontinuation;
- To demonstrate reductions in ticagrelor blood levels Δ [ticagrelor] with the intraoperative use of DrugSorb™-ATR;
- To establish the safety of the intraoperative use of DrugSorb™-ATR in the intended population.

The hypothesis is that, for patients undergoing cardiothoracic surgery with CPB within two days of ticagrelor discontinuation, the intraoperative use of the DrugSorb™-ATR device will significantly reduce postoperative bleeding as measured by a ranked composite endpoint of clinically meaningful bleeding metrics: 1) fatal perioperative bleeding, 2) moderate, severe, or massive bleeding events based on the Universal Definition of Perioperative Bleeding in Cardiac Surgery (UDPB) ≥ 2 classification, and 3) 24-hour chest tube drainage (CTD).

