Bleeding events are to be recorded as AE/SAEs by the Investigator or designee and will be classified according to the Universal Definition of Perioperative Bleeding (UDPB) in adult cardiac surgery. [17] Classifications are based on criteria presented in **Table 1** and will be determined based on the relevant data entered within the eCRFs. Of note, UDPB counts transfusions of PRBCs, platelets, FFP, and Cryoppt beginning at chest closure. While intra-operative transfusions of these blood products prior to chest closure will be documented, they will not be counted as part of the UDPB classification or contribute to the primary endpoint. Preoperative transfusions are not counted in the UDPB classification. Transfusions of PCC and rFVIIa are counted beginning at the start of the procedure for UDPB. Measurement of CTD volume begins at chest closure for UDPB classification. All bleeding event AEs classified as moderate, severe, or massive (Classes 2, 3 or 4) based on UDPB criteria will be referred to the CEC for adjudication of UDPB bleeding class. Details on the process for adjudication and relevant definitions are provided in the CEC Charter.

Postoperative Ischemic Events:

Postoperative ischemic events occurring during the index hospitalization will be captured as safety endpoints in this study. This is with the intent of evaluating any potential risk for ischemic rebound in the setting of ticagrelor removal. Postoperative ischemic events include myocardial infarction (MI), stroke, and urgent coronary revascularization. Of note, given the occasional complexities of distinguishing ischemic from hemorrhagic stroke (i.e., ischemic with hemorrhagic conversion), *all* postoperative strokes occurring during the index hospitalization will be captured within the safety endpoint.

All reported safety events occurring within 30 days of the study procedure that meet programmed criteria for cardiac ischemia or stroke will be submitted to the CEC for endpoint adjudication. All coronary revascularization procedures (regardless of open or percutaneous) that occur post-index procedure and during the follow-up period will be adjudicated by the CEC for the potential safety endpoint of *urgent coronary revascularization*. Details on endpoint definitions, adjudication criteria, and all other CEC processes/procedures are detailed in the CEC charter.

Postoperative Mortality or AEs Resulting in Death

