### 1.1. Study Objectives

- To demonstrate reductions in postoperative bleeding with the intraoperative use of DrugSorb™-ATR in patients undergoing cardiothoracic surgery with CPB within two days of ticagrelor discontinuation
- To demonstrate reductions in ticagrelor blood levels  $\Delta[\text{ticagrelor}]$  with the intraoperative use of DrugSorb™-ATR
- To establish safety of the intraoperative use of DrugSorb™-ATR in the intended population

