### **5 STATISTICAL ANALYSIS METHODS**

#### **5.1 General Considerations**

Unless otherwise specified, all statistical analyses will be performed on the mITT population.

In general, summary statistics (n, mean, SD, median, minimum, and maximum for continuous variables, and number and percentage of subjects in each category for categorical variables) will be provided by treatment. All summary tables will be based on the observed data unless specified otherwise. Source data for the summary tables and statistical analyses will be presented as subject level data listings.

The two-sided significance level of 5% is used for the hypothesis testing, unless specified otherwise.

Fixed sequence testing procedure will be utilized to compare the effectiveness of the treatment vs control in the following order:

Primary endpoint → Key secondary endpoint → Additional Secondary endpoints (24hr CTD → platelet transfusions → PRBC transfusions → UBPB events by class → surgical re-exploration for excessive bleeding → fatal perioperative bleeding event)

The significance for the secondary endpoints will only be considered if the primary endpoint is declared statistically significant and the p-value of the previous endpoint is less than 5%, otherwise, the testing procedure stops, and all the subsequent p-values will be nominal.

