## 6 SAFETY ANALYSES

### 6.1 General Considerations

All safety endpoints will be analyzed by treatment on the SA and i-CABG SA populations unless specified otherwise. All safety data will be listed on the SA Population.

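### Safety is to be established, but SAP 6.4 plans only counts and percentages for mortality and ischaemic events; at 65 to 70 per arm, equal low counts leave an excess of about 5 to 9 points not excluded

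*SAP*

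**What the plan says.** Safety is one of three stated objectives. SAP 1.1 has "To establish safety of the intraoperative use of DrugSorb™-ATR in the intended population", and protocol 4.1 has "To establish the safety of the intraoperative use of DrugSorb™-ATR in the intended population". Protocol 9.2.1 explains why postoperative MI, stroke and urgent revascularisation are captured as safety endpoints: "This is with the intent of evaluating any potential risk for ischemic rebound in the setting of ticagrelor removal".

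The planned analysis is as follows.

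- SAP 6.4: "The descriptive statistics will be presented by treatment group and overall, for the following additional safety endpoints". The list covers 30-day cardiac and all-cause mortality, and adjudicated bleeding, stroke, MI and urgent revascularisation up to the 30-day follow-up. Listings are added.
- SAP 5.1: summary statistics are, in general, "number and percentage of subjects in each category for categorical variables".
- SAP 6.1: "All safety endpoints will be analyzed by treatment on the SA and i-CABG SA populations unless specified otherwise".
- SAP 6.3: serious device-related events are summarised by arm.
- Protocol Synopsis: "All AEs occurring after the start of the CPB procedure will be listed and summarized using descriptive methodology". Protocol 11.6 specifies frequency and percentage.

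Neither document states a safety hypothesis, a margin, a between-arm difference or a confidence interval for these endpoints.

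The categorical bleeding endpoints are handled differently. SAP 5.4.2.2 (UDPB ≥3 and UDPB ≥4) and SAP 5.4.2.3 (re-exploration and fatal bleeding within 48 hours) plan Fisher tests, rates by arm, and odds ratios with 95% CIs.

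**The concern.** The objective is worded as something to be shown, but the output for the most serious harms is two columns of counts. When events are few, the arms can look alike by chance, and nothing in the planned table tells the reader how large a difference remains possible. That matters most for the ischaemic events, because the protocol itself names a mechanism by which removing ticagrelor might cause them.

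Rarity does not explain the gap. Fatal bleeding, assumed at 3.0% in both arms in the sample-size tables, does get a between-arm estimate with an interval. As written, the plan quantifies uncertainty for the bleeding outcomes and leaves it unquantified for mortality and ischaemic events.

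**Working it through.** **1. The plan's own figures.** No safety power or precision figure is stated, so there is none to reproduce. The sample size was set on the primary effectiveness endpoint, and it does reproduce:

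- Allowing for dropout as in SAP 2: 130 / (1 − 0.07) = 139.8, so 140 randomised.
- Simulating the Finkelstein-Schoenfeld test with the SAP 5.2.2.1 statistic (4,000 runs, independent components) gives 91.7% power at 65 per arm with SD 500 (SAP Table 1: 92.1%), and 99.7% at 57 per arm with SD 253 (SAP Table 1: 99.7%).

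**2. Inputs for the safety check.** The arm size is 70 as randomised (protocol Synopsis) and 65 as evaluable for the primary endpoint (SAP 2). The size of the safety population is not stated; these two values are taken as its range. Observed counts are set equal in the two arms at 0, 1, 2 or 3. No control event rate has to be assumed.

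**3. Formula.** For x events in n subjects, p = x/n and z = 1.96. The Wilson limits l and u are

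[p + z²/(2n) ± z·√(p(1−p)/n + z²/(4n²))] / (1 + z²/n).

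The Newcombe upper limit for device (1) minus control (2) is

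(p₁ − p₂) + √[(u₁ − p₁)² + (p₂ − l₂)²].

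**4. Worked case: 2 v 2 at 70 per arm.** p = 2/70 = 0.0286, l = 0.0079 and u = 0.0983. The upper limit is 0 + √[(0.0983 − 0.0286)² + (0.0286 − 0.0079)²] = √(0.0697² + 0.0207²) = 0.073, or +7.3 points.

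**5. Results.** Upper 95% limit for the excess risk on the device, in percentage points:

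| Events in each arm | 70 per arm | 65 per arm |
|---|---|---|
| 0 v 0 | +5.2 | +5.6 |
| 1 v 1 | +6.3 | +6.8 |
| 2 v 2 | +7.3 | +7.8 |
| 3 v 3 | +8.1 | +8.6 |

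**6. What the reader would see.** For two strokes in each arm of 70, the current plan prints 2 (2.9%) and 2 (2.9%). With an interval added, the same data read: difference 0.0 points, 95% CI −7.3 to +7.3. An excess of more than twice the observed rate (7.3 / 2.9 = 2.5) is still compatible with the data, and only the second presentation shows it.

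The i-CABG safety set is a subset, so its limits are wider if any subjects have other surgery.

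**The case against.** Several points on the other side have weight.

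- **No rule turns equal counts into a safety claim.** A reader might infer that the plan would declare the device safe if no excess were visible. No passage says so. What stands is that such a reading is possible and that nothing in the plan guards against it.
- **Most of the operative wording is already modest.** The protocol's design statement (Synopsis) and its primary safety endpoint (4.3.5) speak of evaluating safety, and protocol Section 3 of assessing it. The strong verb sits mainly in the objectives.
- **Safety does not rest on counts alone.** There is blinded investigator causality assessment, adjudication of deaths and ischaemic events by the Clinical Events Committee, device-effect tables, laboratory summaries and DSMB review. These are real safeguards, so it would be wrong to say that the conclusion can rest only on not seeing a difference. None of them, however, gives a numerical bound on excess risk.
- **Part of mortality is compared.** Protocol 9.2.1 counts fatal bleeding as cardiac death, and fatal bleeding within 48 hours gets an odds ratio with CI. That is correct, but it is an effectiveness analysis and does not touch stroke, MI, revascularisation or other deaths.
- **Table shells are in a separate document (SAP 8), and the SAP 5.1 definition applies only in general.** The absence of intervals is therefore shown for the SAP text, not for the shells.
- **Anyone can compute the interval from the counts.** This is true, but a report meant to support a safety objective should not leave that step to the reader.

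A reader might also infer that the trial fails for want of a powered safety test. The documents do not support that. No such test is planned, any miss rate would depend on control rates that the documents do not give, and descriptive safety reporting is reasonable at this size. Nor do they support calling ischaemic harm the main trade-off: the protocol calls rebound a potential risk and does not name it in its device-specific risk list (5.1).

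**Conclusion.** The point holds as a gap in reporting, not as an error in the design. Mortality and ischaemic endpoints get counts and percentages with no between-arm difference or interval, alongside an objective to establish safety. With equal counts of 0 to 3 per arm, an absolute excess of about 5 to 9 percentage points is not excluded (+5.2 to +8.1 at 70 per arm, +5.6 to +8.6 at 65). Similar counts could be read as safety without showing it.

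The figures assume 65 to 70 subjects per arm in the safety population, equal observed counts, and the Newcombe method. Unequal counts would shift the limits in either direction. The primary effectiveness result and the data collected are unaffected.

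**What to change.** 1. In SAP 6.4, for each listed endpoint, and in SAP 6.3 for serious device-related adverse events, report the device-minus-control risk difference with a two-sided 95% CI (Newcombe or Miettinen-Nurminen; name one). Present it as estimation only, with no test and no margin.
2. In SAP 6.1, state that similar observed counts are not evidence of no harm, and that the safety summary will give, for each endpoint, the largest excess not excluded (the upper 95% limit).
3. Optionally, at the next amendment, align the verb in the objectives (protocol Synopsis, 1.5 and 4.1; SAP 1.1) with the evaluate and assess wording that the protocol already uses. Protocol Section 16 limits simple notification to changes unrelated to objectives or endpoints, so this step may need the full amendment process. Items 1 and 2 do not depend on it.

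The cost of items 1 and 2 is one table column and a few lines of SAP text, with no extra subjects or data. The downside is that the wide intervals become visible and the safety claim becomes more modest.
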